## SYNOPSIS

**TITLE:** A Phase 1 (First-In-Human [FIH]), Multi-Site, Dose Escalation and Expansion Study of WTX-330 in Adult Patients with Advanced or Metastatic Solid Tumors or Lymphoma

**BRIEF TITLE:** A first-in-human study of WTX-330 to assess safety and determine the recommended dose in adult patients with advanced or metastatic solid tumors and lymphoma

**SPONSOR:** Werewolf Therapeutics, Inc.

**CLINICAL PHASE:** 1

**INVESTIGATION TYPE:** Oncology

**STUDY TYPE:** Dose escalation and expansion study

**PROTOCOL NUMBER:** WTX-330x2101

**INVESTIGATIONAL PRODUCT:** WTX-330

### **STUDY PURPOSE AND RATIONALE:**

The recent development of immuno-oncology agents that enhance antitumor immunity is rapidly changing the treatment of cancer. However, these agents are not effective in all tumor types or in all patients with a certain tumor type. This gap represents an unmet medical need for novel immunotherapy approaches.

Interleukin-12 (IL-12) is a potent, pleiotropic cytokine known to enhance immune-mediated killing of cancer cells. The mechanism of action of IL-12 includes stimulation of both innate and adaptive immune cells. Antigen-presenting cells (APCs) such as dendritic cells and macrophages produce IL-12 upon activation. Binding of IL-12 to its receptor expressed on multiple immune cell types activates the Janus kinase-signal transducer and activator of transcription (JAK/STAT) signaling pathway to induce changes in gene expression. IL-12 signaling activity induces interferon gamma (IFN $\gamma$ ) and together, these two cytokines produce a broad range of immunological activities including induction of T helper type 1 (Th1) cell differentiation; activation of cytotoxic natural killer (NK) and T cells; and inhibition or reprogramming of immunosuppressive cells such as tumor-associated macrophages (TAM) and myeloid-derived suppressor cells (MDSCs). IL-12 also enhances antigen presentation by APCs, which is necessary to stimulate immune responses in tumors that have not naturally generated antitumor immunity.

Numerous studies demonstrate that IL-12 has robust antitumor activity in a range of preclinical models and induces immune memory. These observations have generated significant interest in developing recombinant human IL-12 (rhIL-12) as a therapeutic agent for cancer. In early clinical studies, systemically administered rhIL-12 demonstrated clinical activity in several tumor types including renal cell carcinoma (RCC), melanoma, and non-Hodgkin lymphoma (NHL). However, systemic administration of rhIL-12 was shown to be toxic, resulting in death of 2 patients in a Phase 2 clinical study and multiple hospitalizations. Additional clinical studies using more

tolerable doses and schedules yielded only modest clinical activity, possibly due to a lack of sufficient exposure of rhIL-12 in the tumor microenvironment (TME).

WTX-330 is a conditionally activated IL-12 prodrug that was designed to address the multiple shortcomings of rhIL-12.

This Phase 1 FIH dose escalation and dose expansion study will investigate WTX-330 as a monotherapy for patients with relapsed/refractory (r/r) advanced or metastatic solid tumors and lymphomas. The patients enrolled in this study will include those demonstrating primary or secondary resistance to immune checkpoint inhibitor (CPI) therapy as well as patients with tumor types for which CPIs are not approved. The FIH study will characterize the clinical safety, tolerability, pharmacokinetics (PK), pharmacodynamics (PD) and preliminary antitumor efficacy of WTX-330.

### **KEY STUDY OBJECTIVES:**

The primary objectives of the Dose Escalation part of this study are the following:

- To evaluate the safety and tolerability of WTX-330
- To determine the maximum tolerated dose (MTD) and/or recommended dose for expansion (RDE) of WTX-330

The primary objectives of the Dose Expansion part of this study are the following:

- To further characterize the safety and tolerability of WTX-330
- To evaluate the antitumor activity of WTX-330 as measured by overall response rate (ORR; complete response [CR] + partial response [PR]) by Response Evaluation Criteria in Solid Tumors (RECIST) 1.1, immune ORR (immune-ORR [iORR]; immune CR [iCR] + immune PR [iPR]) by immune RECIST (iRECIST), or Lugano classification (Cheson et al., 2014) for lymphomas

The secondary objectives of this study are the following:

- To characterize the PK profile of WTX-330 (i.e., both parent compound and free IL-12)
- 
- 
- To evaluate the immunogenicity of WTX-330 (i.e., the potential to generate an anti-drug antibody [ADA] response)
- 

## **STUDY DESIGN:**

This is a Phase 1, FIH, multi-site study starting with dose escalation of WTX-330 (Part 1) followed by dose expansion of WTX-330 (Part 2) in two arms (A and B).

### **Dose Escalation (Part 1)**

The dose escalation part of the study will be conducted in patients with relapsed/refractory (r/r) advanced and/or metastatic solid tumors. Patients with primary CNS malignancies are ineligible. Patients with castrate-resistant prostate cancer (CRPC) and non-Hodgkin lymphoma (NHL) will be eligible for Dose Expansion (see Arm B below) but are not eligible for Dose Escalation. During dose escalation, WTX-330 will be administered as a single agent on Days 1 and 15 (i.e., every 2 weeks, Q2W) of 28-day treatment cycle.

The starting dose of WTX-330 is 0.016 mg/kg. Selection of the starting dose in this FIH clinical study was informed by safety and PK data from non-Good Laboratory Practice (GLP) and GLP toxicological studies in cynomolgus monkeys, pharmacology studies in tumor-bearing mice, and the prior clinical experience with rhIL-12. A total of eight provisional dose levels are defined for the dose escalation. A dose level with a 50% lower dose than the starting dose is also included if the first dose level is not tolerated.

To minimize the number of patients treated at potentially subtherapeutic dose levels, cohorts will enroll a minimum of 3 patients and up to 6 patients. In each dose cohort, a minimum of 3 patients are required to have completed the dose-limiting toxicity (DLT) observation period before initiating enrollment of the subsequent cohort.

To help ensure patient safety, dosing of the first 2 patients at each dose level will be staggered by at least 7 days and dosing of the second and all following patients will be staggered by at least 2 days. The DLT assessment period for a dose cohort must be completed and the data reviewed by the Dose Escalation Committee (DEC) prior to the recruitment of patients into the next dose cohort. The DEC is comprised of the study Investigators, the Sponsor's medical representative(s) and independent functional experts as required.

Patients may receive WTX-330 for as long as they continue to show clinical benefit, as assessed by the Investigator, or until disease progression or other treatment discontinuation criteria are met. No intrapatient dose escalation is allowed.

A Bayesian Logistic Regression Model (BLRM) incorporating escalation with overdose control (EWOC) will be used to guide the dose escalation ([Appendix F](#)). Data from patients satisfying the requirements for inclusion in the dose-determining set (DDS) will be included in the model. After completion of a dose cohort, or at any time the BLM is updated, a decision to escalate and the actual dose and schedule selected will be determined by the DEC based on a review of all available clinical, PK and laboratory data and on the recommendation of the BLM regarding the highest admissible dose according to the EWOC principle.

Dose escalation will continue until determination of the MTD and/or RDE. Once the MTD/RDE is identified, the Dose Expansion part of the study (Part 2) will open. Determination of the RDE and selection of an optimal dosage will be informed not only by clinical PK, PD, antitumor activity and safety data, but also by nonclinical pharmacology and toxicology data.

## Dose Expansion (Part 2)

Patients in Dose Expansion will have a confirmed diagnosis of a r/r locally advanced or metastatic solid tumor or lymphoma for which the patient has progressed or is intolerant of standard therapy, or for whom no standard therapy with proven benefit exists. Dose Expansion (Part 2) will be conducted in 2 arms that will enroll the following patient populations:

- **Arm A:** Patients with indications for which a CPI is indicated/approved (e.g., cutaneous malignant melanoma, RCC, non-small cell lung cancer [NSCLC], head and neck squamous cell carcinoma [HNSCC], urothelial carcinoma, etc.) who have been treated with a CPI regimen and who demonstrate primary or secondary resistance to CPI therapy. Primary resistance is defined as disease progression or stable disease (SD) < 6 months as the best response after at least 6 weeks of exposure to inhibitors of PD-(L)1. Secondary resistance is defined as disease progression  $\geq$  6 months after initiation of PD-(L)1 inhibitors in patients who have received clinical benefit (i.e., CR or PR or SD > 6 months). Patients who discontinue CPI therapy for toxicity or other reasons and who don't demonstrate primary or secondary resistance to CPIs as defined here are not eligible. Patients with Hodgkin lymphoma are also ineligible.
- **Arm B:** Patients with tumor types for which CPI therapy is not indicated/approved (e.g., pancreatic cancer, microsatellite-stable [MSS] colorectal carcinoma, castrate-resistant prostate cancer [CRPC], NHL) and who are CPI naïve. Patients with NHL should have either follicular lymphoma or diffuse large B-cell lymphoma (DLBCL), though other subtypes of NHL including T-cell lymphomas may be considered after a discussion with the Sponsor. All patients with NHL must have received at least 2 prior systemic therapies. Patients with primary CNS malignancies are not eligible.

Additional arms may be added in the Dose Expansion for specific indications of interest.

Patients will remain on study treatment until they experience unacceptable toxicity, progressive disease per RECIST ([Appendix D; Eisenhauer et al., 2009](#)) or iRECIST ([Appendix E](#)) for solid tumors, or confirmed progressive disease for NHL (dose expansion part) according to Lugano classification ([Cheson et al., 2014](#)), and/or treatment discontinued at discretion of the Investigator, or the patient withdraws consent.

The study consists of a screening period, a treatment period with either Dose Escalation (Part 1) or Dose Expansion (Part 2), an End-of-Treatment (EOT) visit, and a safety follow-up period. The Safety Follow-Up Visit should occur either 30 days after the last dose of study drug or prior to the start of a new cancer regimen, whichever comes first. Overall survival status will be evaluated every 12 weeks (+/- 2 weeks) for patients who are on Dose Expansion (Part 2). Patients will be contacted via telephone to evaluate overall survival until initiation of a new therapy or death, whichever comes first.

The end of the study is defined as when 80% of patients have either discontinued the study or have completed follow-up. Throughout the study, patients will be assessed for efficacy, PK, PD and safety of WTX-330.

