4.2. Final Analyses

One final planned primary analysis will be performed after the completion of the following sequential steps:

1. All subjects have completed the study as defined in the protocol.
2. All required database cleaning activities have been completed, and final database release and database freeze has been declared by Data Management.

5. Analysis Sets

Analysis Set	Definition / Criteria	Analyses Evaluated
Screened Subjects	All subjects who provided informed consent.	
 • Disposition
Enrolled Subjects	All subjects who provided informed consent and met all study eligibility criteria as recorded in the eCRF.	
 • Disposition
Safety Analysis Set	This will include all patients who received at least 1 dose of WTX-330 and had at least 1 post-baseline safety assessment. Safety analyses will in general be descriptive and will be presented in tabular format with the appropriate summary statistics for the Safety Analysis Set. The safety set will be the primary population for all safety related endpoints except determination of the dose-DLT relationship.	
 • Demographics • Cancer history • Exposure and compliance • Previous and concomitant therapies • Safety evaluations except for DLT
Dose-determining (DDS) Analysis Set	This will include all patients in the safety set who have either (a) experienced a DLT at any time during Cycle 1, or (b) completed Cycle 1 without experiencing a DLT. The DDS, which is the analysis set used for determination of the MTD, will consist of patients who have met the minimum treatment and safety evaluation requirements of the study, and/or who experience a DLT during Cycle 1. The minimum treatment and safety evaluation requirements will have been met if, in Cycle 1, the patient received 75% of assigned study treatment dose, completed the required safety evaluations for Cycle 1, and did not experience a DLT. Patients who do not meet these minimum treatment and safety evaluation requirements will be regarded as ineligible for inclusion in the DDS and will be replaced, if	
 • DLT events

QMS Document Name: Statistical Analysis Plan Template(EN)	Page 10 of 41
QMS No (include version ref): STF-015-GL.03	Document date: 14JUL2022
CONFIDENTIAL	

Analysis Set	Definition / Criteria	Analyses Evaluated
	needed, until the minimum number of patients required for evaluation is reached.	

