8.2.1. Individual Time Point Response

According to RECIST 1.1, the time point response will be evaluated as Complete Response (CR), Partial Response (PR), Stable Disease (SD), Progressive Disease (PD), Not Evaluable (NE). According to iRECIST, the time point response will be evaluated as Immune unconfirmed progressive disease (iUPD), Immune confirmed progressive disease (iCPD), Immune complete response (iCR), Immune partial response (iPR), Immune stable disease (iSD), Not Evaluable (NE). According to Lugano classification, the Lugano (Metabolic/PET-CT Based) time point response will be evaluated as Complete Response (CR), Partial Remission/Response (PR), Stable Disease (SD), and Progressive Disease (PD).

The following RECIST 1.1, iRECIST 1.1, and Lugano time point response(s) will be excluded from derivation of Best Overall Response (BOR), Clinical Benefit Rate (CBR), Duration of Response (DOR), Progression free Survival (PFS), Immuno Best Overall Response (iBOR), Immuno Clinical Benefit Rate (iCBR); Immuno Duration of Response (iDOR), Immuno Progression free Survival (iPFS):

- All RECIST 1.1, iRECIST 1.1 and Lugano time point response(s) after Antineoplastic therapy (including radiotherapy, surgery and medication) will be excluded
- For RECIST 1.1 and Lugano, any time point response(s) after the first PD will be excluded
- For iRECIST, any time point response(s) after the first iCPD will be excluded

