8.2.7. Overall Survival (OS)

Overall survival (OS) is calculated from the date of first WTX-330 dose to the date of death. The subjects without death during study will be censored at the date of last known alive.

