8.3.5. Analysis of Time to Events

Time to event parameters (DoR, iDoR, PFS, iPFS, OS) will be estimated using the Kaplan-Meier method (Kaplan & Meier, 1958). The number and percentage of subjects with events/censored, the 1st quartile (25%), median, 3rd quartile (75%), and their 2-sided 95% confidence interval, event-free rate at 3/6/9/12/15 months and their 2-sided 95% confidence interval will be presented.

Event or censor category of each subject in the summary for DoR, iDoR, PFS, iPFS will be presented. Event categories include progression and death. Censor categories include No progression and death, Progression or death after antineoplastic therapy, Progression or death after two or more missing assessment.

Kaplan-Meier curves for PFS, iPFS and OS of expansion cohorts will be plotted.

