Safety and Survival Status Follow-Up
Safety Analysis Set

Dose Escalation: WTX-330 0.016 mg/kg (Phase Therapy: Dose level and/or Arm/Disease)

Subject ID/Age/Sex	Date of Contact (Study Day)	Subject Status	Date of Last Known to Be Alive (Study Day)	New Surgery or Therapy?: Radiotherapy/Antineoplastic Surgery/Anticancer Medications	Continuing in Survival Monitoring?
XXXX-XX/xx/M	DDMMYYYY (xx)	Alive	DDMMYYYY (XX)	No	Yes
	DDMMYYYY (xx)	Lost to follow up			
XXXX-XX/xx/F	DDMMYYYY (xx)	Alive	DDMMYYYY (XX)	Yes: XXXXXXXXXXXX/ /XXXXXXXXXXXXXXXXXX	Yes
	DDMMYYYY (xx)	Alive	DDMMYYYY (XX)	Yes: / / /XXXXXXXXXXXXXXXXXX	Yes
	DDMMYYYY (xx)	Dead			
XXXX-XX/xx/M	DDMMYYYY (xx)	Alive	DDMMYYYY (XX)	No	Yes
	DDMMYYYY (xx)	Alive	DDMMYYYY (XX)	Yes: XXXXXXXXXXXX/ /	Yes
	DDMMYYYY (xx)	Lost to follow up			

Note: Study day = Assessment date - Date of Day 1 + 1 if assessment date is on/after the first WTX-330 dose; Study day = Assessment date - Date of Day 1 if assessment date is before the first WTX-330 dose.

Programming Note:

* Sorting order is by Subject ID, and Date of Contact.

Listing 16.2.2.3
Death
Safety Analysis Set

Dose Escalation: WTX-330 0.016 mg/kg (Phase Therapy: Dose level and/or Arm/Disease)

Subject ID/Age/Sex	Date of Death (Study Day)	Primary Reason for Death	Death Period
XXXX-XXX/xx/M	DDMMYYYY (xx)	Disease Progression	Death within 30 Days of last study drug
XXXX-XXX/xx/F	DDMMYYYY (xx)	Adverse Event: #1, #4	Death within 30 Days of last study drug
XXXX-XXX/xx/F	DDMMYYYY (xx)	Unknown	Death within 30 Days of last study drug
XXXX-XXX/xx/M	DDMMYYYY (xx)	Other: XXXXXXXXXXXXXXXXX	Death after 30 Days of last study drug

Note: Study day = Assessment date - Date of Day 1 + 1 if assessment date is on/after the first WTX-330 dose; Study day = Assessment date - Date of Day 1 if assessment date is before the first WTX-330 dose.

Programming Note:

- * Sorting order is by Subject ID.
- * Repeat each dose level and/or arm on a separate page.

Listing 16.2.3
Deviations from the Clinical Protocol
Safety Analysis Set

Dose Escalation: WTX-330 0.016 mg/kg (Phase Therapy: Dose level and/or Arm/Disease)

Subject ID/Age/Sex	Date of Protocol Deviation (Study Day)	Protocol Deviation Term	Protocol Category	Major/Minor
XXXX-XXX/xx/M	DDMMYYYY (xx)	XXXXXXXXXXXXXXXXXXXXXXXXXXXXXXXXXXXX	XXXXXXXXXXXXXX	Minor
XXXX-XXX/xx/F	DDMMYYYY (xx)	XXXXXXXXXXXXXXXXXXXXXXXXXXXXXXXXXXXX	XXXXXXXXXXXXXXXXXXXXXXXXXXXXXX	Minor

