Note: Study day = Assessment date - Date of Day 1 + 1 if assessment date is on/after the first WTX-330 dose; Study day = Assessment date - Date of Day 1 if assessment date is before the first WTX-330 dose.

Programming Note:

* Sorting order is by Subject ID, Visit.

Listing 16.4.5.1.2
WTX-330 Administration - Part 2 of 2
Safety Analysis Set

Dose Escalation: WTX-330 0.016 mg/kg (Phase Therapy: Dose level or Arm/Disease)

Subject ID/Age/Sex	Visit	WTX-330 Administered/ Reason Not Done	Infusion		Actual Dose (mg/kg) / Total Volume (mL)	Dose Adjustment?/ Adjustment Type	Reason for Adjustment
			Interrupted?/ Reason for Interruption	Time of Interruption/ Restart Time			
XXXX-XXX/xx/F	C1D1	Yes	No		XX/XXX	No	
	C1D15	No, COVID-19 Related					
	C2D1	Yes	No		XX/XXX	Yes/ Dose Missed	Adverse Event: #x
	C2D15	Yes	Yes/Infusion Reaction	HH:MM/HH:MM	XX/XXX	No	
	C3D1	Yes	No		XX/XXX	Yes/Dose Reduced	PI/Sponsor Decision
	C3D15 <insert>	No, Other: XXX					
XXXX-XXX/xx/M	C1D1	Yes	Yes/Other: XXXXXX	HH:MM/No	XX/XXX	Yes/Dose Discontinued	Other: XXXXXXXX

Programming Note:

* Sorting order is by Subject ID, Visit.

Listing 16.4.5.2.1
Antineoplastic Therapy since Discontinuation of Study Treatment - Medication
Safety Analysis Set

Cohort	Dose level or Arm/Disease	Subject ID/Age/Sex	Line of Therapy	Agent	Therapy Start Date	Therapy Stop Date
Dose Escalation	WTX-330 0.016 mg/kg	XXXX-XXX/xx/M	1	XXXXXXXXXXXXXXXXXXXX	DDMMYYYY	DDMMYYYY
				XXXXXXXXXXXXXXXXXXXX	DDMMYYYY	DDMMYYYY
			2	XXXXXXXXXXXXXXXXXXXX	DDMMYYYY	Ongoing
				XXXXXXXXXXXXXXXXXXXX	DDMMYYYY	DDMMYYYY
			3	XXXXXXXXXXXXXXXXXXXX	DDMMYYYY	DDMMYYYY
		XXXX-XXX	1	XXXXXXXXXXXXXXXXXXXX	DDMMYYYY	DDMMYYYY

Programming Note:

* Sorting order is by Cohort, Dose level or Arm/Disease, Subject ID, Line of Therapy, Agent.

Listing 16.4.5.2.2
Antineoplastic Therapy since Discontinuation of Study Treatment - Radiation
Safety Analysis Set

Cohort	Dose level or Arm/Disease	Subject ID/Age/Sex	Site of Radiation	Start Date	End Date
Dose Escalation	WTX-330 0.016 mg/kg	XXXX-XXX/xx/M	Adrenal Gland	DDMMYYYY	DDMMYYYY
			Bile duct	DDMMYYYY	DDMMYYYY
			Bronchus	YYYY	YYYY
		XXXX-XXX/xx/M	Gall bladder	Unknown	Unknown
			Large Intestine	DDMMYYYY	DDMMYYYY
		XXXX-XXX/xx/F	Other: XXXXXXXX	DDMMYYYY	DDMMYYYY

Programming Note:

* Sorting order is by Cohort, Dose level or Arm/Disease, Subject ID, Start Date, Site of Radiation.

Listing 16.4.5.2.3
Antineoplastic Therapy since Discontinuation of Study Treatment - Surgery
Safety Analysis Set

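### Survival calls in the expansion part stop at new therapy, while the SAP analyses overall survival to death

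*Protocol*

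**What the plan says.** Protocol Synopsis, Study Design, closing paragraphs of Dose Expansion (Part 2): survival status is checked every 12 weeks (± 2 weeks) in Part 2 only. The next sentence sets when the calls end: "Patients will be contacted via telephone to evaluate overall survival until initiation of a new therapy or death, whichever comes first". The same section gives the end-of-study rule: "The end of the study is defined as when 80% of patients have either discontinued the study or have completed follow-up".

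Protocol Synopsis, Efficacy Analyses: OS is censored when the patient was last known to be alive. New therapy is not named as a censoring event.

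SAP 8.2.7: OS runs from first dose to death, and "The subjects without death during study will be censored at the date of last known alive". Again new therapy is not mentioned.

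SAP 8.2.1, for tumour-response outcomes: "All RECIST 1.1, iRECIST 1.1 and Lugano time point response(s) after Antineoplastic therapy (including radiotherapy, surgery and medication) will be excluded". The outcomes it covers are BOR, CBR, DOR, PFS and their immune versions. OS is not among them.

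SAP 8.3.5: OS is estimated by Kaplan-Meier with quartiles, and "event-free rate at 3/6/9/12/15 months and their 2-sided 95% confidence interval will be presented". Curves are planned for the expansion cohorts.

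TFL shells, Listing 16.2.2.2: each survival contact records any new therapy and has a column headed "Continuing in Survival Monitoring". Mock rows show new therapy recorded, monitoring still marked Yes, further contacts, and in one case a later death.

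**The concern.** The SAP analyses OS as time to death from any cause, regardless of later treatment. The synopsis collects survival only up to the next treatment. A patient who starts new therapy and is no longer called will have a last-known-alive date close to the start of that therapy, so the analysis censors the patient there although no document says that it should.

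Starting new therapy usually follows progression, which worsens prognosis, and depends on being fit enough, which improves it. Either link makes the censoring informative. The planned OS medians and 3- to 15-month rates would then not estimate overall survival, and their confidence intervals would not show it, because those intervals reflect sampling error only. Survival status that was never collected may not be recoverable at analysis.

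**Working it through.** **Step 1: the texts side by side.**

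| Place | What ends OS observation |
|---|---|
| Protocol Synopsis, Part 2 follow-up | New therapy or death (telephone contact) |
| Protocol Synopsis, Efficacy Analyses | Death, or last known alive |
| SAP 8.2.7 | Death, or last known alive |
| SAP 8.2.1 | New therapy cuts off response-based outcomes; OS not listed |
| SAP 8.3.5 | Censoring category for antineoplastic therapy given for DoR, iDoR, PFS and iPFS; not for OS |
| Listing 16.2.2.2 (mock rows) | Contacts and a death after new therapy |

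Where the SAP wants new therapy to end observation, it says so. For OS it does not. Only the rule on telephone contact stops there.

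**Step 2: how large could the effect be?** The plan states no OS event count, rate or power, so there is no figure to reproduce. Every input below is an assumption except the arm size of up to 20 (SAP 3.2).

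Base case: median time to progression 3 months; death hazard 0.02 per month before progression and 0.12 after; new therapy starts 1 month after progression in 20, 40 or 60% of patients; data cut-off uniform between 12 and 24 months after first dose.

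True 12-month OS can be checked by hand. With progression hazard λ = ln 2 / 3 = 0.231, h0 = 0.02 and h1 = 0.12:

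S(12) = exp(−12(λ+h0)) + [λ/(λ+h0−h1)] × [exp(−12·h1) − exp(−12(λ+h0))]
= 0.049 + 1.763 × (0.237 − 0.049) = 0.38.

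Simulation (400,000 patients per scenario) then compares Kaplan-Meier with full follow-up against follow-up stopped at new therapy. Share of deaths missed = 1 − (deaths observed) / (all deaths before cut-off). Results are for 20/40/60% uptake.

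| Scenario | Deaths missed | 12-month OS, full follow-up | 12-month OS, as estimated |
|---|---|---|---|
| Base case | 15/31/46% | 38% | 40/42/45% |
| Fitter patients get new therapy (post-progression hazard 0.08, others 0.20) | 12/26/41% | 29/34/39% | 26/30/36% |
| Hazard 0.08 throughout | 12/23/35% | unbiased | unbiased |
| Base case, 75% of later deaths learned of elsewhere, survivors censored at new therapy | 4/8/12% (0.25 × base) | 38% | 37/36/35% |

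In the base case a 20-patient arm has about 16 deaths, of which 2.4/4.9/7.3 are missed. Median OS of 9.4 months is estimated as 9.7/10.1/10.8.

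The base case is biased upward because stopping calls removes progressed patients, who have the higher hazard. In the second scenario it removes the better-prognosis patients among those who have progressed, so the sign reverses. In the last, late deaths are counted while matching survivors are not, which biases OS downward.

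**Step 3: sensitivity.** In a grid of 243 combinations (uptake, time to progression, both hazards, lag to new therapy), 7 to 52% of deaths are missed. Median OS shifts by about 0 to +3 months, typically +0.4. All shifts are upward because the grid gives treated and untreated patients the same post-progression hazard.

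A separate set of assumptions (median progression 2.5 months, uptake 30 to 70%, therapy half a month later, 24-month cut-off) varies post-progression survival:

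| Median post-progression survival, with / without new therapy | True median OS | Estimated median OS |
|---|---|---|
| 10 / 3 months | 8.0–10.8 | 7.5–9.9 |
| 6 / 6 months | 9.9 | 10.6–12.6 |
| 3 / 10 months | 8.0–10.9 | 14.2–15.2 |

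**Step 4: against sampling noise.** With 20 patients and full follow-up in the base case, the estimated median ranges from 5.4 to 14.0 months (2.5th to 97.5th percentile) by chance alone. The base-case bias of 0.3 to 1.4 months (9.7 − 9.4 to 10.8 − 9.4) is well inside that range.

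**The case against.** **The analysis rules agree.** The synopsis and SAP 8.2.7 both censor at last known alive, so the telephone rule can be read as a limit on data collection, not a contradiction in analysis. That is a fair description, but it does not remove the problem: the collection rule determines when a patient was last known alive.

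**The listing rows are mock data.** They are headed Dose Escalation, where no OS calls are required, and other mock rows are plainly not rules (Listing 16.2.7.5 puts a Grade 1 event in a Grade 2-or-higher category). This stands: the shell shows intent at most. The shells are, however, to be run for Arms A and B as well. If the columns mirror the eCRF, contact after new therapy may already be happening, and then the synopsis sentence is the part to correct.

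**No OS summary is in the current shells.** The table and figure lists contain none; OS appears only per patient in Listing 16.2.6.2. The shells' modification history says that outputs were selected for the aCSR. This lowers the immediate impact, but SAP 8.1 and 8.3.5 still plan OS tables and curves.

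**Only the synopsis is visible.** The protocol body or Schedule of Assessments may continue contact. The synopsis sentence on 12-weekly status has no new-therapy stop of its own, and nothing says that deaths learned of by other routes are discarded. All of this stands and is why the finding is conditional.

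**The endpoint is minor and the size unknown.** OS is secondary, untested and measured in small mixed-tumour arms without a control. Primary ORR and safety analyses are unaffected. This limits the weight of the point. An unknown direction is no comfort, though, because a reader cannot adjust for it.

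**Conclusion.** The concern holds as a conditional one. The synopsis ends Part 2 survival calls at new therapy, the SAP's OS definition does not, and following the call rule as written may censor OS informatively.

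Neither the size nor the direction can be fixed from the documents. Under the assumptions shown, about 7 to 52% of deaths would be missed. Bias in 12-month OS ranges from none to several percentage points either way in the named scenarios, and bias in the median from about −1 to +7 months across the more extreme assumptions. In one 20-patient arm the base-case bias is smaller than sampling variation.

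The plan should be changed, but this does not threaten the trial's primary conclusions. Confidence is medium, because the protocol body was not available.

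**What to change.** 1. **Protocol:** state that survival status in Part 2 is collected every 12 weeks until death, loss to follow-up, withdrawal of consent or end of study, regardless of new anticancer therapy. If the protocol body already says this, correct only the synopsis sentence.
2. **SAP 8.2.7:** add that OS is not censored at new therapy, and label any analysis that is so censored as a sensitivity analysis. Start dates are already planned for output, for example in Listing 16.4.5.2.1 ("Antineoplastic Therapy since Discontinuation of Study Treatment - Medication").
3. **End of study:** define completed follow-up for Part 2 in the 80% rule, and check it against SAP 4.2, whose first condition for the final analysis is "All subjects have completed the study as defined in the protocol".
4. **If calls have already stopped for some patients:** report per arm how many were censored at new therapy and how many later deaths are known.

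Cost: one protocol amendment, one SAP sentence, and 12-weekly calls for up to about 40 patients (2 arms × 20). Longer follow-up may delay the 80% trigger and hence study end and the final analysis, which is why item 3 belongs with item 1.
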